# Patients who are unable to tolerate carboplatin and etoposide, may discontinue induction and receive the maintenance regimen.

\* Recommended premedications. Alternative institutional standards may be used. Consider minimizing use of corticosteroids due to immunomodulatory effects. Entinostat is taken 1 hour before and 2 hours after a meal.

\*\*If there is no infusion-related reaction after the initial dose, all subsequent doses of atezolizumab can be infused over 30 ( $\pm 10$ ) minutes.

\*\*\*Doses and volume of diluent per institutional standard.

PO = Orally, IV = Intravenous, AUC = Area Under Curve

Regimen Description – Maintenance (Cycle 5-17) #					
Agent	Premedication; Precautions*	Dose	Route	Schedule	Cycle Length
Entinostat	Take on an empty stomach (at least 1 hour before and 2 hours after a meal)	Assigned dose level	PO	Day 1, 8, 15	21 days (3 weeks)
Atezolizumab		1200 mg	IV infusion over 30 ( $\pm 10$ ) minutes**	Day 1	

# Patients who are unable to tolerate carboplatin and etoposide, may discontinue induction and receive the maintenance regimen. If this occurs, maintenance may begin prior to Cycle 5 and can continue for a total of 1 year of treatment.

\* Entinostat is taken 1 hour before and 2 hours after a meal.

*\*\*If there is no infusion-related reaction after the initial dose, all subsequent doses of atezolizumab can be infused over 30 ( $\pm 10$ ) minutes.*

*PO = Orally, IV = Intravenous, AUC = Area Under Curve*

### Drug dose calculations

Height and weight should be obtained and recorded on Cycle 1 Day 1. Body surface area (BSA) calculations should be performed using institutional standards and AUC calculations using the Calvert formula (see Section 6.2.3.1). The treatment plan weight should be adjusted if patient experiences a >10% change in body weight and drug doses should be recalculated accordingly.

#### 6.1.1 Entinostat

Entinostat will be taken once daily on days 1, 8, 15 of a 21-day cycle. On day 1 when patient receives additional therapy, entinostat will be administered prior to other chemotherapy or immunotherapy agents. For many patients, the ideal time to take entinostat may be 2 hours after breakfast so that patients can be assessed on day 1 treatment days before their entinostat dose. Attempts should be made to take entinostat near the same time of day on days 8 and 15, but it may be taken at any time during the scheduled calendar day (24-hour period of 12:00 AM to 11:59 PM).

When taken with food, entinostat has demonstrated a food effect; exposure is significantly reduced when entinostat is administered with a high fat meal. Accordingly, entinostat is to be administered on an empty stomach, at least 1 hour before and 2 hours after a meal. Tablets should not be split, crushed, or chewed. Missed or vomited doses should not be made up.

Entinostat is known to cause nausea and vomiting. To reduce the incidence of nausea and vomiting associated with entinostat administration, subjects will receive an institutional specific 5-HT3 receptor antagonist prior to taking the dose of entinostat.

Administration of entinostat is contraindicated in patients with a history of allergy to entinostat or other medications that have a benzamide structure (e.g., tiapride, remoxipride, clebropride).

Careful monitoring of patients for signs of infection or reactivation of past infections is recommended, as reactivation of infection has been reported in patients treated with entinostat, in some cases without evidence of neutropenia (Gojo *et al.*, 2007). The clinical significance of this finding and the potential association with entinostat is unknown.

#### 6.1.2 Atezolizumab

Administration of atezolizumab will be performed in a setting with emergency medical facilities and staff who are trained to monitor for and respond to medical emergencies.

The initial dose of atezolizumab will be delivered over 60 ( $\pm 15$ ) minutes. If the first infusion is tolerated without infusion-associated AEs, the second infusion may be delivered over 30 ( $\pm 10$ )

minutes. If the 30-minute infusion is well tolerated, all subsequent infusions may be delivered over 30 ( $\pm 10$ ) minutes.

Institutional standards should be followed for the infusion of atezolizumab and monitoring for infusion reactions.

Atezolizumab treatment may continue after completion of the study according to investigator/patient discretion as standard of care.

### 6.1.3 Carboplatin

Carboplatin will be administered on Day 1. Carboplatin at the appropriate dose will be given intravenously as a 30-60 minute infusion in Dextrose 5% in Water or Sodium Chloride 0.9%, volume per institutional standard.

#### 6.1.3.1 Carboplatin Dose Calculation and Administration

Carboplatin dose will be calculated using the Calvert formula:

Total Dose (mg) = target AUC\* (GFR+25), GFR may be substituted by Creatinine Clearance (CrCl) calculation.

**Note:** Calculated total dose is in mg – not mg/m^2

The CrCl (replaces GFR in Calvert formula) will be calculated for each treatment course using the Cockcroft-Gault formula:

$$CrCl = \frac{(140 - age) * weight(kg)}{72 * serum\ creatinine} * (0.85\ if\ female)$$

The minimum serum creatinine value used will be 0.7 mg/dL and a CrCl cap will be 125 mL/min. Questions about this calculation should be directed to the PI.

**Note:** Remember to re-calculate the dose for each treatment cycle based on current creatinine value. The actual body weight should be used for all calculations. (As stated above in Section 6.1, the treatment plan weight should be adjusted if patient experiences a >10% change in body weight and drug doses should be recalculated accordingly.)

Carboplatin dose rounding is allowed as per institutional guidelines.

### 6.1.4 Etoposide

Etoposide will be administered at a dose of 100 mg/m^2 IV over 60 minutes on Days 1-3 of each cycle. Preparation of each agent, administration instructions, and order of infusions should follow institutional policy.

Etoposide dose rounding is allowed as per institutional guidelines.

## 6.2 Definition of Dose-Limiting Toxicity

Management and dose modifications associated with the above adverse events are outlined in Section 7.

Dose limiting toxicity (DLT) is defined as the occurrence of any of the following toxicities listed below. The DLT period will be from Cycle 1, Day 1 through the first cycle. To be evaluable for a DLT, at least 66% of the prescribed dose of each drug must be received during cycle 1 (i.e., 2 of 3 doses of entinostat must be received or 66% of prescribed carboplatin, etoposide, or atezolizumab dose must be infused to be considered evaluable if no DLT occurred). If treatment-related adverse events result in <66% of drug doses received, patients will be evaluable for DLTs. Any toxicities attributable to cancer or cancer progression will not be considered DLTs.

DLTs if felt to be possibly, probably, or definitely related to entinostat:

- Less than 66% of entinostat (0 or 1 doses) received during the first cycle due to treatment-related adverse event(s)
- Death in the absence of progressive cancer (Any grade 5 adverse event)
- Any adverse event resulting in discontinuation of carboplatin/etoposide chemotherapy prior to Cycle 2
- Any treatment-related toxicity causing delay of more than 3 weeks from planned cycle 2 day 1
- Any  $\geq$  Grade 3 non-hematologic adverse event (non-laboratory), excluding alopecia, uncontrolled nausea or vomiting. Grade  $\geq 4$  uncontrolled nausea or vomiting should be considered a DLT if it persists  $\geq 72$  hours despite maximal medical management.
- Any  $\geq$  Grade 3 non-hematologic laboratory value if medical intervention is required (not including endocrinopathies requiring hormone replacement) or leads to hospitalization

DLTs regardless of relatedness to entinostat (attribution to any study drug):

- Hematologic events
  - Grade  $\geq 4$  febrile neutropenia
  - Grade 4 neutropenia lasting  $>7$  days
  - Grade 3 thrombocytopenia associated with bleeding requiring transfusion or Grade  $\geq 4$  thrombocytopenia.

Dose escalation will proceed within each cohort of 3 patients according to the following scheme. Dose-limiting toxicity (DLT) is defined above.

Escalation/De-escalation Rule												
Number of patients treated	1	2	3	4	5	6	7	8	9	10	11	12
Escalate if # of DLT $\leq$	0	0	0	0	0	0	1	1	1	1	1	1
Deescalate if # of DLT $\geq$	1	1	1	1	2	2	2	2	3	3	3	3
Eliminate if # of DLT $\geq$	NA	NA	2	3	3	3	4	4	4	5	5	5

The study team will review adverse events as listed above that occur outside the DLT window, events that lead to treatment discontinuation, or other adverse events of clinical concern attributed to entinostat on an ongoing basis throughout the trial. If frequent or serious events are noted in a cohort, the study team may close a cohort to enrollment and proceed with the above design but allocating patients only to dose levels below the closed cohort.

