## 9. STATISTICAL CONSIDERATIONS

### 9.1 Study Design/Endpoints

This is a phase 1 trial to evaluate the safety and efficacy of various doses of entinostat combined with atezolizumab, carboplatin, and etoposide therapy for patients with treatment naïve ES-SCLC. Four dose levels of entinostat are detailed in Figure 1. The Bayesian optimal interval (BOIN) design will be used to find the maximum tolerated dose (MTD) based on safety (Liu and Yuan, 2015; Yuan et al., 2016). The target toxicity rate for the MTD is 20%. Due to overlapping hematologic toxicities between chemotherapy and entinostat, it may be difficult to separate attributions specifically to entinostat, particularly for thrombocytopenia events. Our DLT definitions will count these more extreme hematologic events at DLTs, although it is recognized that these occur in the setting of carboplatin and etoposide chemotherapy alone. Therefore, it is anticipated that a 20% DLT rate is a conservative estimate of the true DLTs directly related to entinostat. Furthermore, small cell lung cancer is an aggressive malignancy with poor overall survival. Additional toxicity is justified if there is potential for efficacy gains. Dose-limiting toxicities (DLT) will be determined by adverse events occurring during the first cycle of treatment. DLTs are defined in Section 6.2.

The primary endpoints of the study are:

- MTD of entinostat
- Grade 3/4 adverse event rate as defined by CTCAE v5.0
- Number of cycles received of the combination of entinostat, atezolizumab, carboplatin, and etoposide (maximum = 4)

The secondary endpoint of the study is:

- 9-month PFS rate, defined as the proportion of patients alive and without disease progression after 9 months from study enrollment

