#### 9.1.1 Treatment allocation

Participants will be enrolled and treated in cohorts of size 3. Only DLTs that occur within the first cycle will be used for dose finding. As shown in Figure 2, the BOIN design uses the following rule, optimized to minimize the probability of incorrect dose assignment, to guide dose escalation and de-escalation.

The steps to implement the BOIN design are as follows: 1) Participants in the first cohort are treated at dose level 1; 2) To assign a dose to the next cohort of participants, conduct dose escalation and de-escalation according to the rule displayed in the table below; 3) Repeat step 2 until the maximum sample size of 36 is reached, or stop the trial if the number of participants treated at the current dose reaches 12 and the decision according to the table below is to stay at the current dose.

After the trial is completed, the MTD is determined based on isotonic regression as specified in Liu and Yuan (2015). This computation is implemented by the shiny app “BOIN” available at <http://www.trialdesign.org>. Specifically, the MTD is the dose for which the isotonic estimate of

[figure not shown]
the toxicity rate is closest to the target toxicity rate. If there are ties, the higher dose level will be selected when the isotonic estimate is lower than the target toxicity rate and the lower dose level will be selected when the isotonic estimate is greater than or equal to the target toxicity rate.

At the conclusion of the trial, all available safety data will be reviewed. If a significant number of clinically significant adverse events outside the definition of a DLT occurred at the MTD, the recommended phase 2 dose may be a lower dose level than the MTD. Examples of clinically significant events that would be considered are events similar to DLTs that occurred in later cycles outside the DLT window, treatment discontinuation due to an adverse event attributed to entinostat, or patient withdrawal from the study due to intolerable adverse events.

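### Under Section 6.2, a Cycle 1 non-hematologic death judged unrelated to entinostat meets no DLT criterion, so the decision table can score it as DLT-free

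*Combined protocol and SAP*

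**What the plan says.** Section 6.2 defines DLTs in two lists.

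- The first is headed "DLTs if felt to be possibly, probably, or definitely related to entinostat". It contains the death bullet, "Death in the absence of progressive cancer (Any grade 5 adverse event", together with the bullets on missed entinostat doses, stopping chemotherapy before Cycle 2, a long delay of Cycle 2, and grade 3 or higher non-hematologic events.
- The second is headed "DLTs regardless of relatedness to entinostat (attribution to any study drug". It contains only febrile neutropenia, prolonged grade 4 neutropenia and thrombocytopenia criteria. It has no death bullet.

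On evaluability, Section 6.2 says: "If treatment-related adverse events result in <66% of drug doses received, patients will be evaluable for DLTs". Section 9.1.1 adds: "Only DLTs that occur within the first cycle will be used for dose finding". The same escalation table appears in Sections 6.2 and 9.1.1 and uses only the number of DLTs and the number of patients treated at the dose.

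The dose table in Section 6.1 gives no entinostat in Cycles 1-4 at Level -1. Objective 1.1.1 is the MTD of entinostat in combination with the other three drugs.

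**The concern.** The words in parentheses in the death bullet cover every grade 5 event, while the heading above restricts the bullet to events at least possibly related to entinostat. If the heading governs, a fatal non-hematologic toxicity assigned only to atezolizumab, carboplatin or etoposide adds 0 to the numerator and 1 to the denominator, which moves the table towards escalation. A non-fatal grade 4 thrombocytopenia due to carboplatin would count. The MTD is a primary endpoint and the table decides which dose the next cohort receives, so the scoring of a death should not depend on how a reader resolves this conflict.

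**Working it through.** **1. Does any criterion catch the event?** Take a Cycle 1 fatal non-hematologic toxicity attributed to atezolizumab and judged unlikely to be related to entinostat.

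- Death bullet: under the entinostat heading, so not met.
- Missed entinostat doses, chemotherapy stopped before Cycle 2, grade 3 or higher non-hematologic event: same heading, so not met. Some of these bullets speak of treatment-related events in general, which repeats the conflict with the heading.
- Any-study-drug list: hematologic only, so not met.

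**2. Is the patient in the denominator?** Entinostat is due on Days 1, 8 and 15, and 2 of 3 doses satisfies the 66% rule. A patient who dies after Day 8 can meet it directly, if the other drugs were given. A patient who dies before Day 8 has received at most 1 of 3 doses, but stays evaluable because a treatment-related event caused the shortfall. The score is 0/1.

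**3. Reproducing the plan's table.** Target φ = 0.20. Assumed BOIN defaults: φ1 = 0.6φ = 0.12 and φ2 = 1.4φ = 0.28.

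- Escalation boundary: ln[(1−φ1)/(1−φ)] / ln[φ(1−φ1)/(φ1(1−φ))] = ln(0.88/0.80) / ln(0.176/0.096) = 0.1572.
- De-escalation boundary: ln[(1−φ)/(1−φ2)] / ln[φ2(1−φ)/(φ(1−φ2))] = ln(0.80/0.72) / ln(0.224/0.144) = 0.2385.
- Elimination: Pr(p > 0.20 | data) > 0.95 with a uniform prior and at least 3 treated.

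All 36 cells of the printed table are reproduced.

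**4. Effect of one uncounted event.**

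| Patients at dose | Death not counted | Death counted |
|---|---|---|
| 3 | 0/3 escalate | 1/3 de-escalate |
| 3 | 1/3 de-escalate | 2/3 eliminate |
| 6 | 0/6 escalate | 1/6 stay |
| 6 | 1/6 stay | 2/6 de-escalate |
| 9 | 0/9 escalate | 1/9 escalate (unchanged) |
| 9 | 1/9 escalate | 2/9 stay |
| 12 | 0/12 escalate | 1/12 escalate (unchanged) |
| 12 | 1/12 escalate | 2/12 stay |

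For the first cohort, at Level 1, the choice between 0/3 and 1/3 is the choice between Level 2 and Level -1 for the next cohort.

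**5. Level -1.** With no entinostat in Cycle 1, relation to entinostat is not possible. Read literally, no Cycle 1 event on the first list, fatal or not, can be a DLT there. The rule that stops the trial when the lowest dose is eliminated could then be triggered at that level only by hematologic events.

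**6. How often it could matter.** The documents give no rate for such deaths. Assume r = 1%, 3% or 5% per patient, the same at every level and independent of other DLTs. The chance of at least one in a cohort of 3 is 1 − (1 − r)³:

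- 1 − 0.99³ = 3.0%
- 1 − 0.97³ = 8.7%
- 1 − 0.95³ = 14.3%

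A 10,000-trial simulation of the design gives average sample sizes of 23.6, 23.8, 22.4 and 19.6 for the four scenarios in Section 9.1.3 (stated: 23.7, 23.7, 22.3 and 19.4). In Scenario 2:

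| Assumed r | Trials escalating directly after a cohort with such a death: not counted / counted | Level 3 selected: not counted / counted |
|---|---|---|
| 1% | 8.1% / 1.4% | 16.7% / 14.6% |
| 3% | 22.0% / 3.8% | 16.7% / 10.9% |
| 5% | 33.7% / 5.6% | 16.7% / 8.3% |

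These figures follow the table mechanically, with no human override. They show sensitivity to r and are not a forecast.

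**The case against.** The strongest reply is that the split is deliberate. Only entinostat changes between levels, the other three drugs are fixed, and Section 9.1 describes the 20% rate in terms of DLTs directly related to entinostat. A death that has nothing to do with entinostat says little about its dose. This may be the intention, and the documents do not prove a drafting slip. They also do not settle the matter: the parenthesis covers any grade 5 event, Objective 1.1.1 concerns the combination, and a test of relation to entinostat cannot work at Level -1.

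Several stronger readings are tempting and are not supported.

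- *Every treatment-related death not attributed to entinostat escapes.* It does not. A fatal hematologic event that meets the second list is a DLT whichever study drug caused it.
- *Attribution will often exclude entinostat.* Section 10.2 defines possible as an event that may be related, and the note closing the entinostat risk list in Section 10.1.1.1 warns that it could worsen the known toxicities of partner drugs. At Levels 1-3 an investigator must judge the relation unlikely or absent despite that warning.
- *Section 9.1 concedes that such attribution is hard.* Its sentence, "it may be difficult to separate attributions specifically to entinostat, particularly for thrombocytopenia events", is about hematologic overlap, which the second list already handles.
- *The trial would automatically escalate after a death.* It would not. Section 6.2 has the team review events leading to discontinuation as well as "other adverse events of clinical concern attributed to entinostat", and lets it close a cohort after frequent or serious events. Section 13.1 requires Principal Investigator sign-off on dose decisions and at least monthly calls that include the CTEP Medical Officer. Section 10.3.3 requires expedited reporting of deaths within 30 days of the last investigational dose, whatever the cause. Section 9.1.1 allows a recommended phase 2 dose below the MTD.

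These safeguards make it unlikely that a death would go unnoticed. None of them turns it into a DLT, so the count that feeds the table and the final isotonic MTD estimate is unchanged.

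**Conclusion.** The point holds in a limited form. On the literal text, a Cycle 1 non-hematologic death attributed to another study drug and judged unlikely or unrelated to entinostat is scored DLT-free with the patient evaluable, and at Level -1 this applies to every non-hematologic Cycle 1 death. One such event can change the table's action at each full-cohort size from 3 to 12, though not at every count. The conclusion rests on the heading governing its bullets. Its practical frequency is unknown and should be low; the 1-5% rates are assumptions. Because the gap is narrow, discretion exists and the split may be intended, this is a should-fix item and not a fatal flaw in the design.

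**What to change.** Reconcile the heading and the grade 5 bullet in Section 6.2 with each other and with Objective 1.1.1, so that a Cycle 1 death attributed to a study drug is not scored as DLT-free by default. State explicitly how relation to entinostat is to be judged at Level -1. Listing grade 5 events with the any-study-drug events is one way to do this; deaths due to cancer would remain excluded by the existing sentence in Section 6.2. If the sponsor intends the entinostat-only reading, the parenthesis should be qualified and the text should say how such a patient enters the numerator and denominator.

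The cost is an edit to one bullet and one clarifying sentence. The decision boundaries depend only on the target rate and cutoff, so the table stands. If grade 5 events move lists, a death due only to a backbone drug would count, making dose finding slightly more conservative: at an assumed 1-3% rate, it adds at most about 1-3 percentage points to the DLT rate at each level.

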## 7.2 Entinostat

### 7.2.1 Dose reductions for entinostat during induction

Dose Level 1	
Dose Reduction	Entinostat Dose
Starting Dose Level	2 mg, PO weekly
1 st Dose Reduction	Discontinue entinostat
PO = Orally	

Dose Level 2	
Dose Reduction	Entinostat Dose
Starting Dose Level	3 mg, PO weekly
1 st Dose Reduction	2 mg, PO weekly
2 nd Dose Reduction	Discontinue entinostat
PO = Orally	

Dose Level 3	
Dose Reduction	Entinostat Dose
Starting Dose Level	5 mg, PO weekly
1 st Dose Reduction	3 mg, PO weekly
2 nd Dose Reduction	2 mg, PO weekly
3 rd Dose Reduction	Discontinue entinostat
PO = Orally	

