### 7.2.3 Management and Dose Modifications for Entinostat

If carboplatin and etoposide are held during induction, entinostat and atezolizumab will also be held.

If at any time atezolizumab is held for atezolizumab-related AEs, instruct the patient to continue to take entinostat and to notify the study team if the event gets worse. If the adverse event worsens, entinostat should then be held with atezolizumab until the adverse event improves as specified in the below management and dose modification tables for both drugs. Entinostat may also be held at the investigator discretion for severe or life-threatening events.

If entinostat is held in either induction or maintenance regimen, the other study drug(s) will also be held, unless the adverse event can clearly be attributed only to entinostat and not to the other study drugs, in which case carboplatin, etoposide, and atezolizumab may be given in accordance with the regimen at the time (i.e. induction or maintenance).

The following specific management and dose modifications will be made for adverse events thought to be at least possibly related to entinostat. Patients requiring a delay of  $> 3$  weeks will discontinue entinostat. Patients that require a dose reduction when already receiving dose level - 1 (2 mg PO, weekly, as per table above) will discontinue entinostat. It is recommended that investigators maximize treatment for nausea, vomiting and diarrhea. No specific entinostat dose reductions are required for anemia.

Neutropenia	Management/Next Dose for Entinostat
≤ Grade 1	No change in dose
Grade 2	Hold* until ≤ Grade 1. Resume at same dose level.
Grade 3	Hold until ≤ Grade 1. Resume at one dose level lower **
Grade 4	Discontinue entinostat ***
* For grade 2 neutropenia events occurring mid-cycle, treatment does not need to be held ** For grade 3 neutropenia events occurring mid-cycle, treatment should be held, but dose reduction not required upon resuming. If event persists to day 1 of next cycle, resuming at one dose level lower is required. *** Entinostat should be held for grade 4 events occurring mid-cycle and may resume at one dose level lower with GCSF support upon recovery to ≤ Grade 1.	
For neutropenia events occurring between days 2 and 21 of each cycle that improve by day 1 of subsequent cycle, dose reductions may be made at investigator discretion. GCSF support should be considered on subsequent cycles.	

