Thrombocytopenia	Management/Next Dose for Entinostat
≤ Grade 1	No change in dose
Grade 2	Hold* until ≤ Grade 1. Resume at same dose level.
Grade 3	Hold until ≤ Grade 1. Resume at one dose level lower
Grade 4	Discontinue entinostat
* For grade 2 thrombocytopenia events occurring mid-cycle, treatment does not need to be held For thrombocytopenia events occurring between days 2 and 21 of each cycle, dose reductions at next cycle Day 1 may be made at investigator discretion, unless required as above	

Other non-hematologic AEs	Management/Next Dose for Entinostat
≤ Grade 2	No change in dose
Grade 3	Hold until ≤ grade 1. Resume at one dose level lower.
Grade 4	Discontinue entinostat

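### Read literally, Section 6.2 counts controlled Grade 3 nausea as a DLT but not uncontrolled Grade 3 nausea under the same bullet

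*Combined protocol and SAP*

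**What the plan says.** Section 6.2 has two groups of DLTs. The first is headed "DLTs if felt to be possibly, probably, or definitely related to entinostat". One of its bullets covers any Grade 3 or higher "non-hematologic adverse event (non-laboratory), excluding alopecia, uncontrolled nausea or vomiting". The add-back follows at once: at Grade 4 or higher, "uncontrolled nausea or vomiting should be considered a DLT if it persists" for at least 72 hours despite maximal management. No sentence excludes controlled Grade 3 nausea, and none makes uncontrolled Grade 3 nausea a DLT. Section 9.1 only refers back to Section 6.2.

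These rules bear on the same patients:
- Section 6.2, first bullet of the same group: receiving 0 or 1 entinostat doses in Cycle 1 because of treatment-related toxicity is a DLT.
- Section 7.2.3: for a related non-hematologic event, Grade 3 means holding entinostat until Grade 1 or lower and resuming one level down. Grade 4 means stopping it.
- Section 7.2.1: at Dose Level 1 (2 mg), the first reduction is "Discontinue entinostat".
- Section 6.1.1 requires a 5-HT3 antagonist before each entinostat dose, and Section 7.2.3 adds: "It is recommended that investigators maximize treatment for nausea, vomiting and diarrhea".
- Section 9.1.1: only first-cycle DLTs enter dose finding, in cohorts of 3. Section 9.1 makes the MTD a primary endpoint.

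**The concern.** The qualifier sits on the wrong side of the exclusion. A Grade 3 event that responds to antiemetics is what the supportive-care rules aim for, yet it is the one counted. The event that resists treatment is left out. Nausea is an expected toxicity here, since Section 6.1.1 says that entinostat causes it.

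The text can be repaired in at least two ways, and they disagree about uncontrolled Grade 3 events. Different investigators could therefore classify the same patient differently. First-cycle DLTs are the only input to the escalation rule and cohorts have three patients, so one classification can decide the next dose.

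**Working it through.** **Step 1. Classify by the text.** The table takes related nausea in Cycle 1 that no other bullet settles. Repair A excludes all nausea and vomiting unless Grade 4 or higher for 72 hours or more despite maximal management. Repair B sets that add-back at Grade 3.

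| Event | Literal text | Repair A | Repair B |
|---|---|---|---|
| Grade 3, controlled | DLT | no | no |
| Grade 3, uncontrolled, 72 h or more despite maximal management | no | no | DLT |
| Grade 4 or higher, uncontrolled, 72 h or more despite maximal management | DLT | DLT | DLT |

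For vomiting the first row is uncertain, because the adjective may qualify nausea only, in which case all vomiting is excluded. The inversion for nausea holds under either parsing.

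**Step 2. Remove the cases that the 0-or-1-dose bullet settles.** Entinostat is given on Days 1, 8 and 15, and missed doses are not made up (Section 6.1.1).
- Level 1, Grade 3, onset before the Day 8 dose: reduction from 2 mg means stopping, so 1 dose; DLT, controlled or not.
- Levels 1 to 3, Grade 4, onset before the Day 8 dose: entinostat stops, so 1 dose; DLT.
- Levels 2 and 3, Grade 3, onset before the Day 8 dose and still above Grade 1 on Day 15: 1 dose; DLT.
- Levels 2 and 3, Grade 3, onset before the Day 8 dose but recovered by Day 15: at least 2 doses; the nausea wording decides.
- Levels 1 to 3, Grade 3, onset after the Day 8 dose: 2 doses already taken; the nausea wording decides, unless chemotherapy is stopped or Cycle 2 is delayed by more than 3 weeks.

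**Step 3. Reproduce the decision table (Section 9.1.1).** Target 0.20. The usual BOIN multipliers 0.6 and 1.4 are assumed, because the protocol does not state them.
- Escalation bound: ln(0.88/0.80) / ln[(0.20 × 0.88)/(0.12 × 0.80)] = 0.157.
- De-escalation bound: ln(0.80/0.72) / ln[(0.28 × 0.80)/(0.20 × 0.72)] = 0.238.
- Elimination: uniform prior, posterior probability above 0.95, at least 3 patients.

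All 36 cells match. At n = 3 the actions for 0, 1 and 2 DLTs are escalate, de-escalate and eliminate. One extra DLT changes the action at 2 of 2 steps at n = 3, 3 of 3 at n = 6, 3 of 4 at n = 9, and 3 of 5 at n = 12.

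**Step 4. First look at Level 1.** Suppose one of the first three patients has controlled Grade 3 nausea after the Day 8 dose. Let p be the Level 1 DLT rate in Section 9.1.3, Scenarios 1 to 3. Not counted: escalate (1−p)³, eliminate 3p²(1−p)+p³. Counted: escalate 0, eliminate 1−(1−p)².

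| p | Escalate, not counted | Escalate, counted | Eliminate, not counted | Eliminate, counted |
|---|---|---|---|---|
| 0.08 | 77.9% | 0 | 1.8% | 15.4% |
| 0.12 | 68.1% | 0 | 4.0% | 22.6% |
| 0.20 | 51.2% | 0 | 10.4% | 36.0% |

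Elimination at Level 1 removes Levels 1 to 3.

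**Step 5. Illustrate the final selection.** The design was rerun with the protocol's table, cohorts of 3, start at Level 1, maximum 36, the stop at 12, and isotonic selection (40,000 trials per setting; 20,000 for the last column). Entries are the percentage selecting the dose whose true rate is 20%.

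| Scenario (dose) | Protocol | Rerun | One first-cohort patient set to DLT | Rerun, given an ordinary first-cohort DLT |
|---|---|---|---|---|
| 1 (Level 3) | 48.64 | 48.5 | 26.6 | 28.9 |
| 2 (Level 2) | 38.13 | 38.9 | 14.0 | 16.0 |
| 3 (Level 1) | 44.92 | 45.0 | 30.0 | 36.7 |

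With the patient set to DLT, selection of Level -1 goes from 2.7% to 19.0%, from 7.7% to 31.3%, and from 29.6% to 59.7%.

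**The case against.** The best defence is that this is a misplaced adjective. An add-back at Grade 4 for 72 hours makes little sense if controlled Grade 3 nausea already counts, so a sensible reader would exclude all nausea and vomiting below that threshold. The affected group may also be nearly empty. Section 6.2 does not define control, and a Grade 3 event that breaks through mandatory prophylaxis could be called uncontrolled. The event must also be attributed to entinostat, most past events were Grade 1 or 2 (Section 2.2.1.5), and Step 2 removes many early cases. Over-counting is cautious in an untested combination. Dose decisions need Protocol PI sign-off, with at least monthly calls that include CTEP (Section 13.1).

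Much of this stands. Frequency cannot be sized and may be zero. A move to Level -1 is not final: 0 DLTs in 3 there leads back to Level 1, with probability 0.97³ = 91%, 0.95³ = 86% and 0.88³ = 68% in Scenarios 1 to 3. Central oversight could impose one reading.

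The defence does not remove the defect. The text states neither repair, and the two repairs differ on uncontrolled Grade 3 events. Sign-off and calls do not say which reading applies. Section 9.1 accepts some over-counting, but it is discussing hematologic events.

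A reader might infer from Step 5 that the wording biases the MTD downward by the amounts shown. The documents do not support that. The last two columns are close, so most of the fall is the design's normal response to any early DLT. At least one such DLT is expected in 22%, 32% and 49% of first Level 1 cohorts (1 minus the not-counted escalation probability in Step 4).

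**Conclusion.** The point holds as a defect of wording in the sole input to dose finding. Under the literal text, related controlled Grade 3 nausea is a DLT and related uncontrolled Grade 3 nausea is not one under this bullet; vomiting is ambiguous. The wording matters for events that start after the Day 8 dose, and at Levels 2 and 3 for earlier events that cost at most one entinostat dose.

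The size per event is clear: at n = 3, one counted event turns escalation into de-escalation, and from Level 1 the next cohort goes to Level -1 without induction entinostat. The size for the trial is unknown, because no rate of Grade 3 nausea by control status is given. The selection percentages illustrate one early DLT and do not estimate bias.

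Two stronger readings should be resisted. One is that the error runs in a single direction. Under Repair A the literal text over-counts controlled events; under Repair B it also misses refractory Grade 3 events, so the direction depends on an intent that the protocol does not state. The other is that uncontrolled Grade 3 nausea escapes the DLT definition altogether. It can still count through missed entinostat doses, stopped chemotherapy or a long delay of Cycle 2.

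**What to change.** The sponsor should confirm its intent and replace the bullet's exclusion and add-back. Suggested text: *excluding alopecia, nausea, and vomiting. Nausea or vomiting counts under this criterion only at Grade 4 or above and lasting 72 hours or longer under maximal medical treatment.* If refractory Grade 3 events are meant to count, write Grade 3 in place of Grade 4. Add that events which are DLTs through another bullet, such as 0 or 1 entinostat doses, are unaffected.

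Apply the new wording prospectively. The Protocol PI and CTEP should review any earlier DLT call that rested on this bullet. They should not reclassify it automatically, because doses may already have been assigned or eliminated on it.

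The cost is one bullet in an amendment, a memo to sites, and that limited review. The decision table and simulations do not change, and adverse events and concurrent medications are already collected.
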